## 2 SYNOPSIS

CCB-CRISIS-01 SYNOPSIS	
IND	149291
Title	The CRISIS Study: A randomized open-label study assessing the safety and anti-coronavirus response of suppression of host nucleotide synthesis in hospitalized adults with coronavirus-19 (COVID-19)
Protocol	CCB-CRISIS-01
Rationale	
Brequinar is a potent DHODH inhibitor that has been studied in more than 1,000 cancer, psoriasis, and organ transplant patients. DHODH inhibition has been extensively studied as a potential therapeutic target in the treatment of RNA-based viruses. The inhibition of DHODH is effective in inhibiting viral replication in pre-clinical models involving many RNA-based viruses with nanomolar potency and a high selectivity index. In these pre-clinical models, the benefit of DHODH inhibition can be reversed by the supplementation of exogenous nucleotides, confirming that the on-target effect of host pyrimidine depletion is key to the anti-viral activity. The primary dose-limiting adverse effects have included thrombocytopenia and mucositis.
 
The CRISIS trial will study standard of care (SOC) and SOC with 5 days of DHODH inhibition. Clear Creek Bio hypothesizes that a defined 5-day course of brequinar will inhibit the enzyme DHODH to a degree sufficient to result in the transient depletion of host pyrimidine nucleotides, thereby inhibiting viral replication. A recent publication demonstrated that inhibitors of DHODH could potentiate the activity of inhibitors of RNA-dependent RNA polymerase (RdRp) in the treatment of dengue virus, another single-stranded RNA virus similar to SARS-CoV-2. This inhibition of viral replication may restore the balance in favor of the host immune system for the clearance of SARS-CoV-2.
 
Marketed DHODHi medications are available, including leflunomide or teriflunomide, however these are very weak inhibitors of DHODH with cellular potency ~500 times lower than brequinar. These low potency inhibitors of DHODH are not expected to have the ability to acutely lower the pool of intracellular pyrimidines to the degree that is required for decreasing the viral load associated with SARS-CoV-2 infection, making brequinar the better choice for acute SARS-CoV-2 infection. Brequinar has not been previously tested as an anti-viral.

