## **6 TRIAL ENDPOINTS**

### **6.1 Primary Endpoint**

- Safety/tolerability measured by rates of post randomization adverse events and hematology/chemistry safety labs.

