## 10 ADVERSE EVENT REPORTING

An adverse event is any untoward medical occurrence in a patient or clinical trial subject administered a medicinal product and which does not necessarily have a causal relationship with this treatment. An AE can therefore be any unfavorable and unintended sign (including an abnormal laboratory finding), symptom, or disease temporally associated with the use of the medicinal product, **whether or not considered related to the medicinal product.**

Events that occur prior to informed consent will be entered as medical history; AEs that occur after informed consent will be entered on the AE form.

Subjects will be questioned and observed for evidence of AEs, whether or not judged by the Investigator or designated person to be related to study drug. All AEs will be documented in the subject's medical record and CRF. For any pre-existing condition or abnormal laboratory finding that changes in severity after dosing, this change should be recorded as an AE. New abnormal laboratory findings that are clinically significant are considered AEs.

All adverse events will be collected from the time of informed consent through Day 15. After Day 15, collect/record only Serious Adverse Events (SAEs) or those judged by the Investigator or designated person to be related to study drug. AE details are to be documented including start and stop date and times, whether continuous or intermittent, severity, any intervention utilized to correct the event (e.g., medication, surgery, or other therapy), outcome and the relationship to the study drug.

AEs identified in the protocol as critical to the evaluation of safety must be reported to the Sponsor by the Investigator according to the reporting requirements within the time periods specified in the protocol.

AEs determined by the Investigator to be related to study drug must be followed until resolution or until they are considered stable or for at least 30 days after discontinuation of study drug.

Any serious adverse events (SAEs) experienced after 30 days post the last dose of study drug should only be reported to the sponsor if the investigator suspects a causal relationship to the study drug.

Abnormal laboratory values or test results occurring after study enrollment constitute AEs only if they induce clinical signs or symptoms, are considered clinically significant, or require therapy.

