Subjects who are discharged from the hospital before Day 7 will have follow up contacts with study staff (phone calls or other digital media) on Days 7, 15 and 29. Early discharge subjects in the brequinar treatment group will also have samples for safety labs (hematology and chemistry) obtained either at the research facility or at an outpatient laboratory on Study Days  $7 \pm 2$  and  $15 \pm 2$ . The safety laboratory results are to be initially assessed in real time by the Principal Investigator or designated person and the Medical Monitor. Any study drug-related clinically significant out-of-range laboratories or study drug-related adverse events will be followed as needed until resolution or stable.

The in-hospital assessments and phone call visits will specifically ask about possible hematologic toxicity including any evidence of the list below. Early discharge subjects will be provided with a list of the following events in lay terms and will be instructed to call the research team if any of these events occur.

PROTOCOL NUMBER: CCB-CRISIS-01  
PROTOCOL VERSION FINAL DATE: 10SEPT2020

Page 45 of 58

- Ecchymosis/purpura/petechiae
- Epistaxis
- Hemoptysis
- Hematuria
- Gingival bleeding
- Prolonged bleeding time from needle sticks, abrasions or lacerations
- Hematemesis
- Rectal bleeding
- Blood in stool
- Any other unusual bleeding noted by the subject or caregiver

Any of these symptoms considered clinically significant will be recorded as an adverse event and must be followed until resolved or stable.

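### Section 10.8 attaches an undefined clinical-significance test to solicited bleeding symptoms that Section 10 would record without one, so mild bleeding may go unrecorded in the adverse event rate

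*Protocol*

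**What the plan says.** Section 10 sets a broad definition: "An AE can therefore be any unfavorable and unintended sign (including an abnormal laboratory finding), symptom, or disease temporally associated with the use" of the product, whether or not it is thought related. The recording rule that follows has no exceptions: "All AEs will be documented in the subject's medical record and CRF". Section 10 does contain a significance test, but for laboratory and test results: "Abnormal laboratory values or test results occurring after study enrollment constitute AEs only if they induce clinical signs or symptoms, are considered clinically significant, or" need treatment.

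Section 10.8 deals with hematologic toxicity. It says "The in-hospital assessments and phone call visits will specifically ask about possible hematologic toxicity including any evidence of the list below", and the list runs from petechiae, nosebleed and gum bleeding through blood in urine or stool to any other unusual bleeding. The list closes with the recording rule: "Any of these symptoms considered clinically significant will be recorded as an adverse event and must be followed until resolved or stable".

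The primary endpoint in Section 6.1 is "Safety/tolerability measured by rates of post randomization adverse events and hematology/chemistry safety labs". Section 11.2 tabulates post-randomization AEs by preferred term, system organ class, severity and relationship. The Synopsis gives the reason for the interest in bleeding: "The primary dose-limiting adverse effects have included thrombocytopenia and mucositis". Section 8.8.3 states that the trial is open label. AEs are graded by CTCAE v4.03 (Section 10.4).

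**The concern.** A nosebleed or petechiae is a sign or symptom, not a laboratory value. Two recording rules therefore cover the same event, and they differ. Under Section 10 it is an AE. Under Section 10.8 it is recorded if someone considers it clinically significant, and nothing is said about the rest. Mild nausea meets no such test; the one symptom group that the protocol chose to ask about does.

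Three things follow if sites act on Section 10.8 as written:

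- Mild bleeding can be asked about, reported by the subject, and still not reach the AE form.
- The threshold can vary between sites (the Synopsis allows up to eight), because no criterion is given.
- The threshold can vary between arms, because the person applying it knows the assignment and knows that the drug can lower platelets. The direction cannot be predicted.

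This is a data-collection rule. A symptom never entered as an AE cannot be put back into the AE table by an analysis plan.

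**Working it through.** The protocol states no figure that depends on this point, so there is nothing to reproduce. The check is a comparison of passages in the protocol dated 10 September 2020, followed by arithmetic on the arm sizes.

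**The two rules side by side**

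| | Section 10 | Section 10.8 |
|---|---|---|
| Covers | any unfavorable sign, symptom or disease | listed bleeding symptoms |
| Significance test | laboratory and test results only | on the symptoms themselves |
| Criterion for significance | not needed for symptoms | none given |
| Events that fail the test | recorded anyway | not addressed |
| Follow-up | drug-related AEs, until resolved or stable or for at least 30 days after the drug is stopped | symptoms judged significant, until resolved or stable, whatever the cause |

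No other section says which rule prevails.

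**What one unrecorded subject does.** Section 7.1 gives about 16 brequinar and about 8 standard-of-care subjects. If a subject's only AE is a bleed that is not recorded, AE incidence falls by:

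- brequinar: 1/16 = 6.25 percentage points;
- standard of care: 1/8 = 12.5 percentage points.

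**Illustration with an assumed count.** Suppose 4 of 16 brequinar subjects have mild bleeding judged not significant, and no one else bleeds. The bleeding rate, with Clopper-Pearson 95% limits, would be:

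- Section 10 rule: 4/16 = 25% (7.3% to 52.4%);
- Section 10.8 rule, read as excluding them: 0/16 = 0% (0% to 20.6%).

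**How likely is it that the rule matters at all?** The chance of at least one subject with mild bleeding among 16 is 1 − (1 − p)^16, where p is an assumed true rate: 56% at p = 5%, 81% at 10%, 97% at 20% and 99.7% at 30%.

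**How much the result depends on assumptions.** Let p now be the true rate of any listed bleeding and s the share called significant. The chance that the table shows no bleeding event in 16 subjects is (1 − p)^16 if all are recorded and (1 − ps)^16 if only the share s is. Both p and s are assumed. The smallest p borrows the 1 mild thrombocytopenia in 39 subjects from Section 3.6.2 as a rough stand-in; it is not a bleeding rate.

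| p | all recorded | s = 50% | s = 20% |
|---|---|---|---|
| 1/39 = 2.6% | 66% | 81% | 92% |
| 10% | 19% | 44% | 72% |
| 20% | 2.8% | 19% | 52% |

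The gap between the rules is modest at the top of this table and large at the bottom. The protocol gives nothing that fixes the row or the column.

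**The case against.** The strongest reply is that Section 10.8 does not contain the word only. It can be read as adding a duty to follow certain symptoms, with Section 10 still requiring every AE on the CRF. Progress notes are also reviewed daily for AEs until discharge (Section 9.5), so a careful site would record every bleed. This stands to the extent that loss of mild bleeding is possible, not certain. It does not remove the problem, because a site following Section 10.8 literally would also be following the protocol.

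A reader might infer that every Grade 1 bleed is left out. The documents do not support that. Nothing equates Grade 1 with not clinically significant, and petechiae in a subject taking a drug with known platelet effects might well be judged significant.

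A reader might also infer that the trial becomes insensitive to its main toxicity. That does not hold either. Thrombocytopenia is measured directly by platelet count. Laboratory results are part of the primary endpoint and are all summarized without a significance filter (Sections 6.1 and 11.2), and hematology is reviewed by the Medical Monitor and the DSMB (Section 10.8). The study-level stopping rule counts Grade 3 or 4 events (Section 8.4.2), which this sentence is unlikely to affect. Section 10.8 presents the symptoms as possible hematologic toxicity; calling them an early sign of it goes beyond the text.

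On size, the nearest experience cited is reassuring: the drug-related AEs listed for five-day dosing at or below 100 mg include no bleeding event (Section 8.2.1). Background bleeding in COVID-19 inpatients, some possibly on anticoagulants (Section 8.10), could be higher, so the true rate is unknown in either direction.

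Open-label assessment affects every AE here. What is particular to this sentence is an undefined threshold that is applied with the arm known.

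**Conclusion.** The inconsistency is real and stands in the current protocol. Section 10.8 puts a subjective, undefined test on symptoms that Section 10 would record without one. Mild bleeding can therefore go unrecorded, and recording can differ by site and arm. The effect falls on the AE-incidence part of the primary endpoint and on the bleeding rows of the AE table.

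The size cannot be stated from the documents. The shifts of 6.25 and 12.5 points per subject follow from the planned arm sizes alone, and apply to overall AE incidence only when the bleed is the subject's sole AE. The other probabilities above rest on assumed bleeding rates, most of them also on assumed shares called significant, and on every site reading Section 10.8 as excluding the remainder. They show that the rule could matter, not how much it will. The point is worth correcting because the correction is small and unrecorded events cannot be recovered later. It does not undermine the trial's safety monitoring.

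**What to change.** Rewrite the closing sentence of the Section 10.8 list to agree with Section 10: any listed bleeding symptom that starts or worsens after consent is recorded as an AE with its CTCAE v4.03 grade, in both arms, whether or not it is considered clinically significant. The existing rule that only onsets after randomization count in the tabulated rate is unaffected.

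Keep the follow-up duty as a separate sentence and do not narrow it. Making clinical significance the general condition for follow-up could cut across the follow-up that Section 10 already requires for drug-related AEs, so both existing requirements should stay.

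The questions are already being asked, so no new procedure is needed. The cost is a few more low-grade AE entries and a slightly higher reported AE rate. Some entries will be noise: with daily blood sampling, bruising at puncture sites would be recorded as ecchymosis. Recording the cause with the event lets such entries be identified.

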### **10.9 Data Safety Monitoring Board**

A Data and Safety Monitoring Board (DSMB) will be established to provide independent oversight to this trial. The primary responsibility of the DSMB will be to review the progress and conduct of the trial in order to maintain scientific rigor and to ensure the wellbeing of subjects participating in the trial. The specific responsibilities of the DSMB will be detailed in a separate DSMB charter. The DSMB will include at a minimum at least one statistician and two clinicians who will perform periodic data review to assess whether there are clinically significant differences between treatment arms that could affect participant safety. Following such a review, the DSMB Chair will advise the Sponsor that the study be stopped, the design changed, or that the study may continue per protocol.

#### **10.9.1 DSMB Safety Review Schedule**

The DSMB is to review adverse events and safety laboratory assessments after the first six subjects complete Day 5 of treatment, and again after the first 12 subjects complete Day 5 of treatment.

PROTOCOL NUMBER: CCB-CRISIS-01  
PROTOCOL VERSION FINAL DATE: 10SEPT2020

Page 46 of 58

## **11 STATISTICAL CONSIDERATIONS**

A separate, detailed statistical analysis plan (SAP) will be finalized prior to locking the database. All analyses will be descriptive in nature and presented by group.

Summaries for quantitative variables will include the mean, median, quartiles, standard error, minimum, and maximum. For qualitative variables, the summaries will include the number and percentage of subjects for each outcome, and 95% confidence interval (CI), when appropriate. Any statistical testing will be considered exploratory and descriptive. All computations will be performed using SAS® (Version 9.4 or higher).

Subject disposition, subject demographics and baseline characteristics will be summarized. Subject data listings will also be provided. The following sections will briefly summarize of the planned statistical analyses and analysis sets for the primary and secondary endpoints.

### **11.1 Study Populations for Analysis**

All analyses will be based on the ITT population, which is defined as all randomized subjects.

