Investigational Product and Dosage	
Subjects will be randomized in a 1:2 ratio to either standard of care (SOC) alone, or SOC + brequinar.
 
Brequinar is available as 100 mg oral capsules. Five once daily doses of brequinar 100 mg are to be administered on Study Days 1 – 5 for those assigned to the SOC + brequinar group.

	Treatment assignment will be randomized, open label.
Primary Objective	
 
To determine the safety and tolerability of SOC and SOC plus brequinar in hospitalized COVID-19 subjects.
 

Secondary Objectives	
 
To determine the rates of/changes in clinical status measures listed through Day 15:                             
 
Hospitalization status
 
Duration of hospitalization
 
NEWS2 Score
 
 
 
Mortality through Day 29
 

Exploratory Objectives	
 
To determine the change in SARS-CoV-2 nasopharyngeal viral load through Day 15
 
To determine the change in inflammatory markers through Day 15
 
To determine the change in DHO levels through Day 15
 
To determine the change in brequinar concentration levels through Day 7
 

Design	
This will be a phase 1a randomized, open label, multi-center study with approximately 24 subjects. All subjects will receive SOC per institutional guidelines for treatment of patients with COVID-19 infection. In addition to SOC, the brequinar group will receive brequinar 100 mg once daily for 5 days.
 
Subjects will have a Screening Visit followed as soon as possible with Study Day 1 (Day 1 may take place on the same day if entry criteria data are available). Study procedures are presented in detail in the procedures section, see below. Subjects will be followed through Day 15. Mortality will be assessed at Day 29.
 
See below for instructions regarding hospital discharge prior to Day 15.
 
Hematology and chemistry results and study information such as NEWS2 criteria are to be collected using the available EHR data as much as possible to avoid extra procedures for the study.

Sample Size:	Approximately 24 subjects will be randomized to either standard of care or standard of care plus brequinar in a 1:2 ratio (approximately 8 assigned to standard of care and 16 subjects on brequinar).
Number of Sites:	1 - 8
Study Period:	An enrollment period of 3 months is expected.

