--	--

	
study drug-related AE or an SAE; the Day 29 mortality assessment is still to take place.
 
If the subject is unable or not permitted to return for planned study visits, the visit activities will be conducted by contacting the subject (phone or other digital media) except for the lab draw. The hematology/chemistry sample will be obtained via outpatient laboratory, if feasible and the results entered into the EDC and reviewed by the study team.
 
Study completion or the reason for study discontinuation will be recorded in the source document and the eCRF. A subject is considered completed the study if they have assessments through Day 15, whether conducted in the hospital or contacted via phone or other digital media.

Safety/ Tolerability
	
Safety/Tolerability
 
Adverse events will be collected from the time of informed consent through Day 15. After Day 15, collect/record only Serious Adverse Events (SAEs) or those judged by the Investigator or designated person to be related to study drug, including but not limited to potential hematologic toxicities. Post-randomization adverse events will be those with an onset after the date and time of randomization.
 
Subjects who develop Grade 3 or 4 toxicities are to be re-evaluated every 2 days, as feasible, until the toxicity returns to Grade <math>\leq 2</math> severity.

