## 8 STUDY TREATMENTS

### 8.1 Description of Study Medications

#### 8.1.1 Brequinar

Brequinar will be supplied as 100 mg capsules. Dosing will be a single 5-day course of brequinar 100 mg once daily for 5 doses. The initial brequinar dose (Day 1) should be administered as soon as possible based on study drug availability from the investigational pharmacy. At least the first dose of study medication is to be taken in the hospital. Subjects in the brequinar group discharged before Day 5 will be dispensed brequinar to take at home daily until all 5 doses have been taken.

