### **11.2 Safety Analyses**

Safety and tolerability will be assessed in terms of AEs, SAEs, NEWS2 Assessments, and safety laboratory data.

Adverse event data will be descriptively evaluated. All AEs will be reported in data listings. The incidence of post-randomization adverse events will be tabulated by MedDRA preferred term and system organ class, and by severity and relationship to study treatment. All laboratory results and NEWS2 Assessments will be summarized using appropriate descriptive statistics.

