### **11.4 DHO and Brequinar Concentration Levels**

DHO and brequinar concentrations levels will be summarized using descriptive statistics.

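### Section 11.1 puts every analysis, including primary safety and brequinar concentrations, on all randomized subjects, so a subject assigned brequinar but never dosed counts in the brequinar safety denominator

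*Protocol*

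**What the plan says.** Section 11.1 defines one population for the whole trial: "All analyses will be based on the ITT population, which is defined as all randomized subjects". It allows no exception, and membership does not depend on having taken study drug.

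Section 6.1 makes safety the primary endpoint: "Safety/tolerability measured by rates of post randomization adverse events and hematology/chemistry safety labs". Section 11.2 describes its analysis: "The incidence of post-randomization adverse events will be tabulated by MedDRA preferred term and system organ class, and by severity and relationship to study treatment". For concentrations, Section 11.4 says only: "DHO and brequinar concentrations levels will be summarized using descriptive statistics". Neither section names a treated, safety or pharmacokinetic set, and none appears in any of the protocol versions shown.

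The synopsis opens the adverse event window at randomization, not at first dose: "Post-randomization adverse events will be those with an onset after the date and time of randomization". Section 8.1.1 says that the first dose "should be administered as soon as possible based on study drug availability from the investigational pharmacy", and Section 9.5 also ties it to the availability of pharmacy staff. Section 9.7 allows withdrawal at any time.

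On numbers, the synopsis says: "Approximately 24 subjects will be randomized to either standard of care or standard of care plus brequinar in a 1:2 ratio", about 8 on SOC and 16 on brequinar.

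**The concern.** The trial's main question is whether brequinar is tolerated. A subject who never takes it says nothing about that, but under Section 11.1 still adds one to the brequinar denominator.

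The protocol leaves room for this to happen. Randomization precedes dosing, and the first dose waits on the pharmacy. Section 8.1.1 requires at least the first dose to be taken in hospital, while eligibility asks only for an expected stay of 24 hours or more. The home supply described for early discharge therefore does not help a subject discharged before dose one.

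In an efficacy comparison, including untreated subjects usually pulls the result toward no effect, which is the cautious direction. For a toxicity rate the same pull favors the drug whenever dosed subjects have more events than undosed ones. At stake are the reported brequinar event rates and the upper confidence limits around them, in an arm of about 16.

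**Working it through.** **Inputs.** Total of 24 subjects, 1:2 allocation (synopsis and Section 7.1). Adverse events counted from randomization (synopsis). All analyses on all randomized subjects (Section 11.1). The number of brequinar subjects never dosed, u, is not given; it is an assumption, taken here as 0 to 4 of 16.

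**The plan's own figure.** 24 × 2/3 = 16 on brequinar and 24 × 1/3 = 8 on SOC. The stated arm sizes reproduce.

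**Expected dilution.** Let p be the event rate in dosed subjects and b the background rate in undosed subjects. The rate seen on all randomized brequinar subjects is

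[p × (16 − u) + b × u] / 16.

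For events that only the drug causes, b = 0 and the observed rate is p × (16 − u)/16. Each undosed subject costs 1/16, about 6%, of the true rate. For all-cause events b is above zero and the loss shrinks. With p = 25%:

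| u | Factor at b = 0 | Observed, b = 0 | Observed, b = 10% |
|---|---|---|---|
| 1 | 0.938 | 23.4% | 24.1% |
| 2 | 0.875 | 21.9% | 23.1% |
| 3 | 0.813 | 20.3% | 22.2% |
| 4 | 0.750 | 18.8% | – |

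For example, at u = 2 and b = 10%: (0.25 × 14 + 0.10 × 2)/16 = 3.7/16 = 23.1%.

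**Zero events observed.** The exact (Clopper-Pearson) 95% upper limit is 1 − 0.025^(1/n):

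| n | 16 | 15 | 14 | 13 | 12 |
|---|---|---|---|---|---|
| Upper limit | 20.6% | 21.8% | 23.2% | 24.7% | 26.5% |

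Section 11.1 gives 20.6% whatever u is. The exposed data support 21.8% to 26.5% for u = 1 to 4.

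**Four affected subjects, all dosed.** On all randomized: 4/16 = 25.0% (exact 95% CI 7.3 to 52.4%). On dosed subjects: 4/15 = 26.7%, 4/14 = 28.6% (8.4 to 58.1%), 4/13 = 30.8%, 4/12 = 33.3% (9.9 to 65.1%).

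At u = 0 every pair of figures coincides.

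**The case against.** Much of the case against stands, and it limits the point.

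*The size is unknown and may be zero.* Randomization and first dispensing both fall on Day 1, subjects are inpatients who can swallow capsules, and those expected to live less than 5 days are excluded. Pharmacy availability is mentioned as affecting timing; nothing says doses will be missed. A reader might infer that the primary estimate is biased toward safety. The documents do not support that: they show a rule that would dilute the rate if anyone goes undosed, with no figure for how many.

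*The direction is conditional.* Undosed inpatients with COVID-19 can also have events. If 4 of 14 dosed subjects and 1 of 2 undosed subjects are affected, the all-randomized rate is 5/16 = 31.3%, above 4/14 = 28.6%. Dilution needs p greater than b.

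*The shifts are small beside the uncertainty.* Moving from 25.0% to 28.6% is minor against intervals running from about 7% to 58%, in a trial that is descriptive throughout.

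*ITT matches the event window.* Counting starts at randomization. Replacing ITT by dosed subjects would drop a brequinar subject who deteriorates before the first dose but keep the SOC counterpart, which could itself make brequinar look safer. This argues for adding an exposed set, not for substituting one.

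*Concentrations.* A reader might infer that undosed subjects lower the mean concentration. That happens only if such a subject is sampled and the value is included; with no sample there is nothing to average.

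*Stopping rules.* Section 8.4.2 uses absolute counts on the brequinar arm, so this denominator does not enter them.

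The objection that an SAP could define a safety set carries less weight. Section 11.1 does not leave the matter open; it covers all analyses, so a treated set in the SAP would contradict the protocol.

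**Conclusion.** The point holds as a correction to a stated rule. Section 11.1 fixes the primary safety analysis on a set that ignores exposure, and the design allows subjects to be assigned brequinar without receiving it. For drug-caused events the relative loss is about 6% per undosed subject among 16. For a zero-event result the upper limit reads 20.6% where dosed subjects would give 21.8% to 26.5%, over an assumed 1 to 4 undosed. The loss is smaller for all-cause events and absent if all are dosed.

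This rests on three things: an arm of about 16, an assumed number undosed, and a higher event rate in dosed than in undosed subjects. It also reads ITT in its usual sense of grouping by assignment. Section 11.1 defines membership only, and Section 11 adds just "All analyses will be descriptive in nature and presented by group", so the handling of a subject who receives the other arm's treatment is not stated.

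The change is worth making before database lock because it is cheap and because choosing an exposed set after seeing open-label data would be harder to defend.

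**What to change.** In Section 11.1, replace the blanket rule as follows:

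- **ITT**, all randomized subjects, for the efficacy analyses of Section 11.3, and kept for an as-randomized table of post-randomization adverse events.
- **Safety set**: brequinar subjects with at least one dose, and SOC subjects, grouped by treatment received, for adverse events and safety labs in Section 11.2. Report it alongside the as-randomized table. List never-dosed subjects with their events, so that pre-dose events are not lost from one arm only.
- **Brequinar concentrations** in Section 11.4: dosed subjects with at least one post-dose sample.

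The cost is a few sentences in Section 11.1, matching text in the SAP, and one additional set of safety tables. No new data are needed: Section 9.5 already has the date and time of brequinar administration recorded, home doses go into a diary, and Section 8.8.5 requires records that show whether a subject received study medication.
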